1 INTRODUCTION

The purpose of this Statistical Analysis Plan (SAP) is to provide detailed descriptions of the statistical methods, data derivations and data displays for study protocol MBPS205 Amendment 5 “A Phase 2b, Multicentre, Multinational, Double-blind, Dose-finding Study, incorporating an open label substudy, in Adult Patients with Type I, III or IV Osteogenesis Imperfecta Treated with setrusumab (BPS804)” dated 12 December 2018. The table of contents and templates for the Tables, Figures and Listings (TFLs) will be produced in a separate document.

Any deviations from this SAP will be described and justified in the Clinical Study Report (CSR).

The preparation of this SAP has been based on International Conference on Harmonisation (ICH) E9¹.

All data analyses and generation of TFLs will be performed using SAS 9.4® or higher.

Note: This plan does not address the validation analyses to the HRpQCT measurements or the pharmacokinetic (PK) analyses. These analyses will be described in a separate analysis plan.

2 STUDY OBJECTIVES

The study is designed to investigate the dose-response to setrusumab in a large cohort of Type I, III and IV OI patients.

2.1 Primary objective

To demonstrate that setrusumab increases radial trabecular volumetric bone mineral density (Tr.vBMD) on high resolution peripheral quantitative computed tomography (HRpQCT) and bone strength on finite element analysis (FEA) in patients with OI Type I, III or IV.

2.2 Secondary objectives

The secondary objectives are:

1. To determine the dose-response relationship of Tr. vBMD to setrusumab after 12 months of treatment
2. To evaluate the onset of treatment effect
3. To evaluate the effect of setrusumab on fracture rate (peripheral, major [long-bone], and vertebral fractures)
4. To evaluate the effect of setrusumab on vertebral fractures and vertebral height
5. To evaluate the effect of setrusumab on bone mineral density (BMD)
6. To evaluate the effect of setrusumab on bone quality
7. To evaluate changes in radial Tr. vBMD on HRpQCT and bone strength FEA during the 12 months post setrusumab treatment period
8. To evaluate the effect of setrusumab on HRpQCT parameters
9. To evaluate the effect of setrusumab on body composition
10. To evaluate the effect of setrusumab on markers of bone composition
11. To evaluate the effect of setrusumab on Patient-Reported Outcomes (PROs) and Quality of Life (QoL)
12. To evaluate the pharmacokinetics (PK) of setrusumab
13. To evaluate potential induction of antidrug antibodies (ADAs) by setrusumab and their effect on safety and PK
14. To evaluate safety and tolerability of setrusumab

2.3 Exploratory objectives

The exploratory objectives are:

1. To evaluate the effect of setrusumab on bone quality
2. To evaluate the effect of setrusumab on changes in use of physical aids
3. To evaluate the effect of setrusumab on hearing

-
4. To evaluate the effect of setrusumab on bone formation and resorption parameters measured by HRpQCT

3 STUDY DESIGN

3.1 General study design

MBPS205 is a phase 2, multicentre, multinational, double-blind, dose range-finding study comparing 3 blinded doses of setrusumab (20 mg/kg, 8 mg/kg and 2 mg/kg) and an open-label treatment arm (20 mg/kg).

[figure not shown]
Following a screening period lasting up to 28 days, eligible participants will be randomised 1:1:1:1 into the 4 treatment arms stratified by OI type (Type I or III/IV) and will receive study treatment (setrusumab) for 12 months. Any participants assigned to placebo according to the previous MBPS205 protocol design will be transferred to open-label 20 mg/kg treatment for 12 months.

Participants will have HRpQCT scans of their non-dominant distal radius at baseline, 3-month (for open-label participants only), 6-month and 12-month time points to determine the effect of treatment on Tr. vBMD. The primary analysis will be conducted once all data up to month 12 has been collected for the blinded treatment groups.

Following completion of the study treatment participants can receive an optional single dose of zoledronic acid and will enter 12 months follow-up period and will have visits at Months 14, 18 and 24 to establish the rate of offset of treatment effect. Participants will also receive follow-up telephone calls at Months 16 and 21. Participants can receive an optional further dose of zoledronic acid at Month 18 at the discretion of their treating physician. During the follow-up period participants will have HRpQCT scans of their non-dominant distal radius and tibia at Month 18 and Month 24.

The Study Flow Chart is presented in Figure 1.

Figure 1: Study Flow Chart

An Independent Data Monitoring Committee will monitor safety throughout the study and make recommendations on the selected dose.

3.2 Randomisation and blinding

3.2.1 Randomisation

All participants will be centrally randomised using an Interactive Web Response System (IWRS) in a 1:1:1:1 ratio to receive either 20mg/kg, 8mg/kg, 2mg/kg or open-label 20 mg/kg stratified by OI type (Type I or III/IV). Subject to informed consent being given by the participant, all participants assigned to placebo prior to protocol amendment 4.0 will be reassigned to begin 12 months of open-label 20 mg/kg setrusumab treatment. ICON Biostatistics will produce a randomisation list that links participant numbers to randomisation numbers. These randomisation numbers will be linked to different treatment regimens and the randomisation scheme will be stratified according to the Sillence Clinical Classification of OI type into 2 groups (Type I or III/IV).

Following confirmation from the investigator, the pharmacist will contact the IWRS and be issued with a treatment regimen. Should the participant be allocated to a setrusumab regimen, then the pharmacist will input the patient's weight into the IWRS and receive a calculated dose per participant.

3.2.2 Blinding

Study Blinding is conducted to ensure that treatment assignment is unbiased and concealed from patients and investigator staff. With the exception of the open-label treatment arm, investigators and participants will remain blinded to each participant's assigned study treatment throughout the course of the study. In order to maintain this blind, an otherwise uninvolved 3rd party (pharmacist) will be responsible for the reconstitution and dispensation of all study treatment. A separate unblinded Clinical Research Associate (CRA) will monitor the pharmacy.

3.2.3 Unblinding

Upon completion of the treatment period (final Month 12 or EOT data collected for the final patient) the blind will be broken and the primary efficacy analysis completed. Analyses for the follow-up period will be carried out separately to the primary analysis once all patients have completed the 12 months follow-up period, or have withdrawn from it.

In the event of a Quality Assurance audit, the auditor(s) will be allowed access to unblinded study treatment records at the site(s) to verify that randomisation/dispensing has been performed accurately.

The IWRS will be programmed with blind-breaking instructions. The study blind may be broken if, in the opinion of the investigator, it is in the participant's best interest to know the study treatment assignment. Mereo must be notified before the blind is broken unless identification of the study treatment is required for a medical emergency in which the knowledge of the specific blinded study treatment will affect the immediate management of the participant's condition (eg, antidote is available). In this case, Mereo must be notified within 24 hours after breaking the blind. The date

and reason that the blind was broken must be recorded in the source documentation and electronic case report form (eCRF), as applicable.

3.3 Study treatments and assessments

During the treatment period study participants will receive 2 mg/kg, 8 mg/kg or 20 mg/kg setrusumab IV, administered monthly for 12 months via 60 minute infusions of 250mL 5% dextrose with setrusumab. Patients randomised prior to Protocol Amendment 4.0 may have received a matching placebo during the treatment period prior to transitioning to open label 20 mg/kg.

Dose changes are not permitted during the treatment period.

The maximum study duration from randomisation to end of the safety follow-up period is 24 months.

A detailed description of procedures and assessments to be conducted during this study can be found in the protocol.

4 STUDY ENDPOINTS

4.1 Primary efficacy endpoint

The primary efficacy endpoint of this study is the change from baseline in Tr. vBMD (radius) on HRpQCT and change from baseline in bone strength on FEA at 12 months.

4.2 Secondary endpoints

The secondary efficacy endpoints of this study are:

1. Tr. vBMD (radius) on HRpQCT at 12 months.
2. Tr. vBMD (tibia & radius) on HRpQCT and bone strength on FEA at 6 months
3. Tr. vBMD (tibia & radius) on HRpQCT and bone strength on FEA at 3 & 6 months in the open-label treatment arm
4. Total fracture rate at 12 months
5. Peripheral fracture rate at 12 months
6. Vertebral fracture rate at 12 months
7. Long-bone fracture rate at 12 months
8. Changes in vertebral fractures and vertebral height with Genant's semi-quantitative method and 6-point quantitative morphometry from baseline at 6 and 12 months
9. Changes in lumbar, whole body, and proximal femur DXA BMD (dual-energy x-ray absorptiometry bone mineral density) (absolute and T-score) from baseline at Month 6 and Month 12
10. Changes in bone histomorphometry
11. Tr. vBMD (tibia & radius) on HRpQCT and bone strength on FEA at 18 and 24 months
12. Changes (tibial and radial) in Total vBMD, cortical vBMD, bone volume fraction (BV/TV), peripheral to medullary trabecular bone density ratio (Met/Inn), trabecular thickness (TbTh), trabecular number (TbN), inhomogeneity, cortical thickness, and cortical porosity from baseline at 6, 12, 18, and 24 months
13. Changes in Tr. vBMD (tibia) from baseline at 12, 18, and 24 months
14. Changes (tibial and radial) in Total vBMD, cortical vBMD, bone volume fraction (BV/TV), peripheral to medullary trabecular bone density ratio (Met/Inn), trabecular thickness (TbTh), trabecular number (TbN), Inhomogeneity, cortical thickness, and cortical porosity on HRpQCT and bone strength on FEA at 3 months in the open-label treatment arm.
15. Changes in body height, weight and body mass index (BMI) from baseline at 6 and 12 months
16. Changes in lean and fat body mass from whole body DXA

17. Changes from baseline at each visit in bone turnover markers and metabolic biomarkers associated with bone including:
 - Parathyroid hormone [PTH]
 - Aminoterminal propeptide of type 1 procollagen [P1NP]
 - Carboxy-terminal propeptide of type 1 procollagen [P1CP]
 - Osteocalcin [OC],
 - Bone-specific alkaline phosphatase [BSAP]
 - Carboxy-terminal telo-peptide [CTX-1]
 - Amino-terminal telo-peptide [NTX-1]
 - Receptor activator of nuclear factor kappa-B ligand [RANKL]
 - Osteoprotegerin
 - Transforming growth factor beta [TGF- β]
 - Sclerostin
 - Released C-terminal pro-peptide of Type V collagen [Pro-C5]
 - Neo-epitope of MMP-2
 - 9 mediated degradation of Type V collagen [C5M]
18. Change in total scores from baseline to Month 6 and 12 on Short Form 12 Health Survey (SF-12), EuroQol 5-dimension 5-level descriptive system (EQ-5D-5L) and Osteogenesis Imperfecta specific Quality of Life Questionnaire for Adults (OIQoLA)
19. Change in OIQoL-A pain and activity subscale scores from baseline to Month 6 and 12
20. Serum concentrations of setrusumab
21. Serum concentrations of anti-setrusumab antibodies
22. Serum concentrations of setrusumab neutralising antibodies
23. Safety and Tolerability endpoints including:
 - Treatment-emergent adverse events (TEAEs)/Treatment-emergent serious adverse events (TESAEs)
 - Infusion site reactions
 - Vital signs
 - Physical examinations
 - ECG
 - Clinical laboratory tests

4.3 Exploratory endpoints

The exploratory endpoints of this study are:

1. Changes in Trabecular Bone Score (TBS) from baseline at 6 and 12 months
2. Changes in usage or need for physical aids from baseline at 12 months
3. Change in auditory function from baseline at 12 months in a subset of patients
4. Change in bone formation from baseline at 6 and 12 months, including:

-
- Normalised newly mineralised bone volume (MV/BV)
 - Normalised newly mineralised surface area (MS/BS)
 - Mineralised thickness (MTh)
 - Normalised formation patch number density (N.F. Patch/BV)
 - Formation patch volume (F.PatchVol.)
 - 3D bone formation rate (3D BFR/BS)
 - 3D mineral apposition rate (3D MAR)
5. Change in bone resorption from baseline at 6 and 12 months, including:
- Normalised newly eroded bone volume (EV/BV)
 - Normalised newly eroded surface area (ES/BS)
 - Erosion depth (ED)
 - Normalised resorption cavity number density (N.R.Cav./BV)
 - Resorption cavity volume (R.Cav.Vol.)
 - 3D bone resorption rate (3D BRR/BS)
 - 3D mineral resorption rates (3D MRR)

5 SAMPLE SIZE AND POWER

The number of participants is based on power considerations for the trabecular vBMD (radius) derived from HRpQCT at Month 12. The primary analysis method for this endpoint will be on the change from baseline within each treatment group, so the primary hypothesis to be tested is

$$H_0: \mu_T \leq 0 \text{ vs. } H_1: \mu_T > 0$$

where μ_T denotes the change from baseline for each dose of Setrusumab. Under the assumptions of a maximum change from baseline of [REDACTED], a standard deviation at both timepoints of [REDACTED] and a correlation between both measurements of [REDACTED] a sample size of 25 patients per group yields approximately 80% power for a one-sided test with significance level 0.025, if the data are analysed on the log scale using a t-test.

For a change from baseline of [REDACTED], with standard deviation as above the one-sided test would have a probability of 80% to yield a p-value below 5%, being considered indicative of a trend.

Following a review of the trabecular vBMD (radius) derived from HRpQCT at Month 6 of those patients within the 20mg/kg Setrusumab open label treatment group, a change from baseline standard deviation of [REDACTED] was observed. This yields to a correlation between baseline and month 6 visits of [REDACTED] (much higher than the [REDACTED] that was originally assumed). If such a correlation is observed at month 12, given 25 subjects per arm, the one-sided test would have a probability of 80% to yield a p-value below 5% for a change in baseline of [REDACTED].

As a secondary analysis, the MCPMod approach will be applied to the data in order to assess a non-flat dose-response curve and to obtain information about the underlying dose-response curve. Due to the missing placebo group, the power of this approach depends heavily on the underlying dose-response curve.

The following candidate models will be used:

- EMax (ED50 of 1.5 mg)
- Exponential ($\delta = 2$)

Under the assumptions of each of the two candidate models being the true dose-response curve, and in addition an Sigmoid EMax model with parameters ED50 = 10 mg and $h = 2.4$, a contrast test at a one-sided significance level of 2.5% has the following power for each of the three models:

Model	EMax	Exponential	Sigmoid EMax
Power	13.7%	73.2%	60.7%

The total sample size required is therefore determined as 100:

- 25 participants on open-label setrusumab (20 mg/kg)
- 25 participants on each of the active arms (2 mg/kg, 8 mg/kg, 20 mg/kg)

Approximately 100 participants will be randomised.

6 ANALYSIS POPULATIONS

Analyses for the primary efficacy endpoints and selected secondary endpoints will be analysed on the FAS, the Non-restricted FAS and the PP samples, while analyses for the remaining secondary efficacy endpoints will be analysed on the FAS sample only. Data collected for patients while taking placebo prior to protocol amendment 4.0 will not be included in any efficacy analysis (i.e. treatment comparisons), however will be included in efficacy descriptive statistic summaries.

Safety and tolerability endpoints will be analysed using the safety population. Data collected for patients while taking placebo prior to protocol amendment 4.0 will be included in all safety summaries.

Pharmacokinetic data will be analysed using the PK population.

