8.2. Method of Treatment Assignment

All participants will be centrally randomised using an Interactive Web Response System (IWRS) in a 1:1:1:1 ratio to receive either 20 mg/kg, 8 mg/kg, 2 mg/kg or open-label 20 mg/kg. Subject to informed consent being given by the participant, all participants assigned to placebo prior to protocol amendment 4.0 will be reassigned to begin 12 months of open-label 20 mg/kg setrusumab treatment. ICON Biostatistics will produce a randomisation list that links participant numbers to randomisation numbers. These randomisation numbers will be linked to different treatment regimens and the randomisation scheme will be stratified according to the Sillence Clinical Classification of OI type into 2 groups (Type I or III/IV).

Following confirmation from the investigator, the pharmacist will contact the IWRS and be issued with a treatment regimen. Should the participant be allocated to a setrusumab regimen, then the pharmacist will input the patient's weight into the IWRS and receive a calculated dose per participant.

Before the study is initiated, the web address for the IWRS and the log in information & directions will be provided to each site.

Study treatment will be dispensed and dosed at the study visits summarised in the Schedule of Activities.

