7.1.4 Definitions relative to safety parameters

7.1.4.1 Adverse Event (AE)

Treatment Emergent Adverse Event (TEAE)

A Treatment Emergent AE (TEAE) is defined as an AE occurring or worsening on or after the first dose of study medication. AEs that occurred for subjects while taking placebo prior to protocol amendment 4.0 will not be considered treatment emergent for the active treatment groups. TEAEs will also be split between AEs that started during the Patient's treatment period and those that start on or after the first day of the follow-up period.

Duration of AEs

The duration of an AE will be calculated as the resolution date minus the start date plus 1.

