8.1.2 Treatment groups

Statistics will be displayed for the following treatment groups:

- Setrusumab 20 mg/Kg
- Setrusumab 8 mg/Kg
- Setrusumab 2 mg/Kg
- Open Label Setrusumab 20 mg/Kg
- Pooled Setrusumub 20 mg/Kg (where applicable)
- Placebo
- Total: overall (where applicable).

Pooled Setrusumub 20 mg/Kg may only be used for the follow-up analysis.

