8.6.1 Adverse events

All AEs will be classified by SOC and PT according to the MedDRA Version 21.1 or higher.

Details for imputing missing or partial start dates of adverse events are described in Section **Error! Reference source not found.**

All AE summaries will be generated by treatment period, follow-up period and overall (i.e including those that started in both the treatment period and follow-up period).

Notes:

- Two AEs with the same PT and classified in the same category (pre-treatment AE or TEAE) will be considered as two different events when calculating the “number of events” in the tables.
- Where a patient has the same AE, based on preferred terminology, reported multiple times in the same category (pre-treatment AE or TEAE), the patient will only be counted once at the preferred terminology level in AE frequency tables.
- Where a patient has multiple AEs within the same SOC in the same category (pre-treatment AE or TEAE), the patient will only be counted once at the SOC level in AE frequency tables.
- AEs where the intensity is missing will be assumed to be “Severe”
- AEs where the causality is missing will be assumed to have “Reasonable possibility of relatedness”

An overall summary of AEs will be provided. The total number of events and number and proportion of patients experiencing any AEs, TEAEs, AEs related to study medication, SAEs, SAEs related to study medication, severe AEs, AEs leading to permanent discontinuation of study treatment and AEs leading to death will be tabulated for each treatment group and overall.

Additionally, TEAEs, related TEAEs, serious TEAEs, related SAEs, severe TEAEs, AEs leading to permanent discontinuation of study treatment and AEs leading to death will be summarised by SOC and PT for each treatment group and overall (number and percentage of patients experiencing at least one AE per PT as well as the number of observed events per PT). All TEAEs will also be summarised separately by maximum severity grade for each SOC and PT and by relationship to study medication for each SOC and PT.

The frequency and incidence of TEAEs will be presented by system organ class and preferred term for each treatment group (number and percentage of participants experiencing at least 1 AE per preferred term as well as the number of observed events per preferred term).

Infusion site reactions will be tabulated and summarised by treatment group and overall.

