8.6.1.1 Adverse Events of Special Interest

The AESIs for setrusumab are:

- Fractures
- Cardiovascular events

The frequency and incidence of all treatment emergent AESIs will be presented by system organ class and preferred term for each treatment group.

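### Adverse event tables set a placebo period cut off by the Amendment 4 switch beside a planned 12 months on active drug, as crude percentages and counts with no adjustment for exposure

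*SAP*

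**What the plan says.** **Placebo in the tables.** SAP section 6 states: "Data collected for patients while taking placebo prior to protocol amendment 4.0 will be included in all safety summaries". SAP 8.1.2 opens its list with "Statistics will be displayed for the following treatment groups", and Placebo is on that list next to the active groups. SAP 7.1.4.1 adds: "AEs that occurred for subjects while taking placebo prior to protocol amendment 4.0 will not be considered treatment emergent for the active treatment groups". The placebo column therefore holds placebo time only.

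**Length of exposure.** Protocol 8.2 states that "all participants assigned to placebo prior to protocol amendment 4.0 will be reassigned to begin 12 months of open-label 20 mg/kg setrusumab treatment". SAP 3.3 says that participants randomised before that amendment "may have received a matching placebo during the treatment period prior to transitioning to open label 20 mg/kg". Neither document says how long placebo lasted or how many participants received it.

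**How events are counted.** SAP 8.6.1 specifies "number and percentage of patients experiencing at least one AE per PT as well as the number of observed events per PT", and "All AE summaries will be generated by treatment period, follow-up period and overall", where overall means treatment and follow-up combined. For fractures and cardiovascular events, SAP 8.6.1.1 says: "The frequency and incidence of all treatment emergent AESIs will be presented by system organ class and preferred term". No adverse event table uses patient-time or a matched window.

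**Collection limits.** The follow-up Schedule of Activities (Protocol section 3) limits reporting after Month 14 to SAEs. Follow-up runs to Month 24.

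**The concern.** A crude percentage of participants with an event rises with time observed. If one column was observed for less time than its neighbours, it shows fewer events even when the underlying rate is the same. Here the shorter column would be placebo, the only non-active reference for the two events of special interest. A reader could see a drug-related excess of cardiovascular events that is only a difference in observation time. For fractures, a true benefit could be hidden.

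The combined tables widen the gap. Placebo has no follow-up period of its own, because those participants' follow-up comes after open-label drug. The active columns gain follow-up time and the placebo column gains none.

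The SAP adjusts for exposure elsewhere: SAP 8.5.1 puts a log-exposure offset in the count models, and SAP 8.5.3.9 annualises the fracture rate. The adverse event tables have no counterpart.

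**Working it through.** The plan gives no adverse event rate, placebo duration or expected ratio, so there is no stated figure to reproduce. The check asks what the tables would show if drug and placebo had the same event rate.

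**Inputs from the documents**
- A month is 28 days (Protocol 6.1), so 13 months are taken as one year.
- Active treatment is planned for 12 months.
- Non-serious events are collected to Month 14 and SAEs to Month 24 (Protocol section 3).
- The original protocol is dated 10 January 2017 and Amendment 4 is dated 18 May 2018 (Protocol Appendix 9).

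**Assumptions**
- The rate is constant and equal on drug and placebo, at 0.3 events per year.
- Placebo lasted 3, 6, 9 or 12 months.

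**How long could placebo have lasted?** From 10 January 2017 to 18 May 2018 is 493 days, and twelve 28-day months are 12 × 28 = 336 days. The dates do not rule out a full 12 months on placebo.

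**Formulas**
- Proportion with an event by month T = 1 − exp(−0.3 × T/13)
- False ratio = active proportion ÷ placebo proportion

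**Active columns**
- 12 months: 1 − exp(−0.2769) = 24.19%
- 14 months: 1 − exp(−0.3231) = 27.61%
- 24 months: 1 − exp(−0.5538) = 42.53%

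**Results with no true difference**

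| Months on placebo | Placebo % | Treatment-period table (active 12 months) | Combined table, non-serious (14 months) | Combined table, SAEs (24 months) |
|---|---|---|---|---|
| 3 | 6.69 | 3.6 | 4.1 | 6.4 |
| 6 | 12.93 | 1.9 | 2.1 | 3.3 |
| 9 | 18.75 | 1.3 | 1.5 | 2.3 |
| 12 | 24.19 | 1.0 | 1.1 | 1.8 |

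**Sensitivity to how common the event is (treatment-period table)**
- 12-month risk of 10%: the ratio is 3.85 at 3 months on placebo, 1.95 at 6 and 1.32 at 9. At only 1 month on placebo it would be 11.4.
- 12-month risk of 90%: 43.8% against 90.0% at 3 months (2.06), 68.4% against 90.0% at 6 (1.32), and 82.2% against 90.0% at 9 (1.09). Percentages saturate, so the distortion shrinks.
- Event counts per participant do not saturate. Their ratio is 12/3 = 4.0, 12/6 = 2.0 and 12/9 = 1.33.

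**Check of the remedy.** At 0.3 per year, 100 participants followed for 3 months give 6.69 first events in 6.69/0.3 = 22.3 patient-years at risk. Followed for 12 months, they give 24.19 first events in 24.19/0.3 = 80.6 patient-years. Both rates are 0.30 per patient-year, a ratio of 1.00.

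**The case against.** **Placebo duration is unknown.** This stands. With 12 months on placebo, the treatment-period table shows no distortion. A reader might infer that setrusumab would look several times less safe than placebo. The documents do not support that as a general statement. In the treatment-period table, a ratio near 3 or above needs about 4 months or less on placebo and an uncommon event (at 4 months, 2.90 for a 12-month risk of 10% and 1.68 for 90%).

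**Active observation is not 24 months in every table.** This also stands. Non-serious events stop at Month 14, so the 24-month column above applies to SAEs only. The treatment-period table covers 12 months and is always produced alongside the combined one.

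**Safety is descriptive and exposure is shown.** SAP 8.6 plans no testing, so no false test result can arise, and SAP 8.4.7.1 summarises exposure by treatment group. But with no test or model, the crude figures are the whole safety result, and a separate exposure table does not turn a percentage for each preferred term into a rate. The derivation is also unclear for switchers. SAP 7.1.4.2 counts from first to last dose of study medication, while SAP 7.1.1 anchors study day to the first non-placebo dose. Placebo time may not be isolated.

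**Dose selection is not affected.** A reader might infer that the choice of dose is biased. It is not biased by this route: the 2, 8 and 20 mg/kg arms each have 12 planned months, and Protocol 11.3 keeps placebo data apart from the comparison of the blinded groups.

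**Fractures are annualised elsewhere.** This is true for the efficacy summaries, but not for the fracture table among the events of special interest. Cardiovascular events have no adjusted summary.

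**Patient-year rates assume a roughly constant hazard.** This stands for front-loaded events such as infusion reactions, and is why the crude percentages should stay.

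**Conclusion.** The concern holds as a defect of presentation. As written, the SAP places a placebo period ended by the Amendment 4 switch beside a planned 12 months or more on active drug, with no time at risk. Under equal true rates the distortion runs against setrusumab whenever placebo exposure was shorter.

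Its size is conditional. At an assumed 0.3 events per year and 3 to 9 months on placebo, the false ratio in the treatment-period table runs from 3.6 down to 1.3, and it disappears at 12 months. In the combined tables, 3 to 6 months on placebo gives about 4.1 to 2.1 for non-serious events and 6.4 to 3.3 for SAEs. Common events show less. These figures rest on a constant, equal hazard and on placebo durations that the documents do not give; the direction does not depend on the particular rate chosen.

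What is at stake is the reading of the only non-active reference column for fractures and cardiovascular events. No hypothesis test and no comparison between doses is affected.

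**What to change.** In SAP 8.6.1 and 8.6.1.1:

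1. Alongside the crude percentages, add first-event incidence and total event rates per patient-year at risk, with 95% CI, for TEAEs, TESAEs and both events of special interest in every column.
2. Define time at risk. Placebo time ends at the switch to open-label drug; active time starts at the first active dose. Time ends at the collection limit for the event type (Month 14 for non-serious events, Month 24 for SAEs) or at earlier withdrawal. For first-event incidence it ends at the event if that comes sooner.
3. Show the placebo N and patient-years in the tables.
4. Drop the placebo column from the follow-up and combined tables.

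The cost is SAP wording, one derived time-at-risk variable from dates already held, and a little more programming. No new data are needed. Because the rates assume a roughly constant hazard, a footnote should say that front-loaded events such as infusion reactions are to be read with the crude percentages.
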